### 4.2. Objectives and Endpoints

The objectives of this addendum are to estimate the effect of starting baricitinib 2-mg on clinical measures during treatment period 1. The data will be analyzed separately from patients in the main protocol.

Secondary objectives for treatment period 2 (Weeks 52 to 104) will be assessed similar to those described in Section 4 of the main protocol; however, as patients in JAHN(7) will not have an originating study baseline, data collected during screening or at Visit 1 of JAHN(7) will be used as baseline for efficacy assessments.

Additional efficacy endpoints will be assessed as exploratory measures and will be described in the statistical analysis plan (SAP). As with the main study, collection of safety data is an important component of this addendum (see Section 9.2 and 9.4 of the main protocol).

| Objectives  | Endpoints  |
|---|--|
| Primary  |  |
| To estimate the effect of starting baricitinib 2-mg on clinical measures and patient-reported outcomes. | 
 
Proportion of patients with a response of IGA 0, 1, or 2 assessed at Week 16
 
   |
| Secondary (Weeks 0-52)   |  |
| To estimate the effect of starting baricitinib 2-mg on clinical measures and patient-reported outcomes. | 
 
Proportion of patients with a response of IGA 0, 1, or 2 assessed at Weeks 4, 24, and 52
 
Proportion of patients with a response of IGA 0 or 1 assessed at Weeks 4, 16, 24, and 52
 
Proportion of patients achieving response of EASI 75 from baseline assessed at Weeks 4, 16, 24, and 52
 
Proportion of patients with a 4-point improvement from baseline of JAHN(7) in Itch NRS at 16 weeks
 
 |

Abbreviation: EASI = Eczema Area and Severity Index; IGA = Investigator's Global Assessment; NRS = numeric rating scale.

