Table of Contents

Appendix		Page
Appendix 1.	Statistical Analysis Plan Addendum	76
Appendix 2.	Statistical Analysis for 4-Month Safety Update.....	92

3. Revision History

Statistical Analysis Plan (SAP) Version 1 is based on Protocol I4V-MC-JAHN(a) (JAHN[a]) and was approved 12 April 2019 prior to the first unblinding. The analyses for Treatment Period 1 of Addendum I4V-MC-JAHN(7) (JAHN[7]) are described in [Appendix 1](#). The analyses for the Withdrawal and Down-titration Substudy of I4V-MC-JAHN (JAHN), for both the main protocol JAHN(a) and addendum JAHN(7), will be described in subsequent versions of this SAP. SAP Version 2 was approved 03 May 2019 prior to the Week 16 database lock (DBL) and includes the following changes:

- *Section 5.1* – separated “responders” into 2 groups: “responders” and “partial responders”
- *Section 6.2.1* – added verbiage to distinguish patients from originating studies: monotherapy studies (I4V-MC-JAHL [JAHL]/I4V-MC-JAHM [JAHM]) and combo therapy study (I4V-MC-JAIY [JAIY])
- *Section 6.2* – updated model to include region; added methods for time to 4-point itch reduction and time to partial response, and aligned Cyclosporine wording to that of originating studies.
- *Section 6.4* – updated censoring rule, updated sensitivity analyses
- *Section 6.8.2* – Baseline Disease Characteristics: Cyclosporine wording updated to “...prior to entry into originating study” and added topical calcineurin inhibitor (TCNI) and vaccine
- *Section 6.9.1* – Background Therapy: added 2 new analyses “Summary of AD Background Therapy” and “Summary of time to initial use of AD background therapy post baseline” (for responders and partial responders)

SAP Version 3 was approved 29 July 2019 prior to the DBL that supports the EU and Japan submissions and includes the following changes:

- *Section 6.2.1* – a Week 36 efficacy evaluable set was defined for Week 36 efficacy and health outcome analyses.
- *Section 6.2.2* – clarified that for step 2 of the Week 16 daily diary window construction, the visit anchor date will be on or before a scheduled visit occurring after Week 16.
- *Sections 6.2.3 and 6.11.1; Tables JAHN.6.6 and JAHN.6.8* – clarified that efficacy and health outcome analyses for the EU and Japan DBL will be done for Weeks 0 through 24, and for Week 36 only descriptive statistics will be included.

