Nonmissing postbaseline efficacy data collected at scheduled visits will be used for analyses. If an assessment is missing at a scheduled visit, an unscheduled postbaseline assessment can be used provided it falls within a ± 4 -day window of the scheduled visit date. If there is more than 1 unscheduled visit within the defined visit window and no scheduled visit assessment is available, the unscheduled visit closest to the scheduled visit date will be used. If 2 unscheduled visits of equal distance are available, then the latter of the 2 will be used. If there is no nonmissing measure collected at the scheduled visit or an unscheduled visit falling within the visit window, the assessment is missing for that scheduled visit.

Diary endpoints were collected up to Week 16 in Period 1 of Study JAHN. Postbaseline daily diary endpoints will be the mean of weekly visit windows (diary windows) anchored on day of first dose (Day 1) for Weeks 1 through 14 as follows:

Week	Days
1	1-7
2	8-14
3	15-21
4	22-28
5	29-35
6	36-42
7	43-49
8	50-56
9	57-63
10	64-70
11	71-77
12	78-84
13	85-91
14	92-98

Week 16 Daily Diary Window Construction

The following sequential steps will be used to determine the Week 16 diary window. The general goal is to anchor on the scheduled Week 16 visit (or a proximal unscheduled visit) if such a visit exists or to use an interval based on days in study for cases where a scheduled Week 16 or a proximal surrogate does not exist.

Step 1: If the Week 16 scheduled visit exists, the Week 16 diary interval is the 7 days prior to the Week 16 date provided that window has at least 4 nonmissing observations. If there are <4 nonmissing observations, the diary window's lower bound will be extended 1 day at a time (up to Day 99) to a maximum of 14 days prior to the Week 16 date until 4 nonmissing observations are obtained. If after extending this diary window's lower bound to 14 days there are <4 nonmissing observations, then go to Step 2.

Step 2: If the Week 16 scheduled visit does not exist, the 7 days prior to the last visit (scheduled or unscheduled) occurring after Day 105 and on or before a scheduled visit occurring after Week 16 will constitute the Week 16 diary window provided that window contains at least 4 nonmissing observations. If there are <4 nonmissing observations, the diary window's lower

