bound will be extended 1 day at a time (up to Day 99) to a maximum of 14 days prior to the unscheduled visit date until 4 nonmissing observations are obtained. If after extending this diary window's lower bound to 14 days there are less than 4 nonmissing observations then go to Step 3.

Step 3: If neither a Week 16 scheduled visit or an unscheduled visit to act as a surrogate for the Week 16 diary window is available, then the Week 16 window will be Day 106 to Day 112. If there are <4 nonmissing observations, the diary window's lower bound will be extended 1 day at a time to Day 99 until 4 nonmissing observations are obtained.

If the steps above do not detect a window with at least 4 nonmissing observations, then the Week 16 window is 7 days from either the Week 16 visit, the surrogate visit, or Day 106 through 112, and the mean is missing and subject to imputation rules.

Week 15 Daily Diary Window Construction

The lower boundary of the Week 15 diary window is defined as Day 99. The upper bound of the Week 15 diary window is the minimum of either Day 105 or the lower bound of the Week 16 diary window -1. Consequently, Week 15 may be <4 days if the Week 16 scheduled visit is before Day 112. Moreover, as the Week 15 diary window cannot exceed 7 days, there could be daily assessments between the Weeks 15 and 16 diary windows that do not fall into a diary window. If after constructing the diary windows there are fewer than 4 nonmissing values, the mean for Week 15 is missing and subject to imputation rules.

PostBaseline

Period 2 (Study Weeks 52-68)

Diary endpoints were collected up to Week 16 in Period 2 of JAHN. For Treatment Period 2, postbaseline daily diary endpoints will be the mean of weekly visit windows (diary windows) anchored on day of the Week 52 visit for Weeks 53 through 66 as follows:

Week of Period 2	Days in Period 2
53	1-7
54	8-14
55	15-21
56	22-28
57	29-35
58	36-42
59	43-49
60	50-56
61	57-63

62	64-70
63	71-77
64	78-84
65	85-91
66	92-98

Week 68 Daily Diary Window Construction

Week 68 daily diary window construction for Period 2 will follow the exact same steps as the window construction for Week 16 in Period 1.

Week 67 Daily Diary Window Construction

Week 67 daily diary window construction for Period 2 will follow the exact same steps as the window construction for Week 15 in Period 1.

Handling of Duplicate Diary Records

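### When the Week 16 visit is missing, Step 2 of the diary rule can anchor on the Week 24 visit, so if diary entries continued, the Week 16 Itch NRS is taken about 8 weeks late

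*SAP*

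**What the plan says.** SAP Section 6.2.2 builds the Week 16 diary window in three steps. The stated goal is to "anchor on the scheduled Week 16 visit (or a proximal unscheduled visit) if such a visit exists", and otherwise to use an interval based on study days.

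- Step 1 uses the 7 days before the Week 16 visit when that visit took place.
- Step 2 covers a patient with no Week 16 visit. Its anchor is the "last visit (scheduled or unscheduled) occurring after Day 105 and on or before a scheduled visit occurring after Week 16". The 7 days before the anchor "will constitute the Week 16 diary window provided that window contains at least 4 nonmissing observations"; failing that, the lower bound moves back day by day, not before Day 99, to a "maximum of 14 days prior to the unscheduled visit date until 4 nonmissing observations are obtained".
- Step 3 is the fallback when no surrogate is available: "then the Week 16 window will be Day 106 to Day 112", extendable back to Day 99.

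The Version 3 entry in the SAP's Revision History describes the same boundary as a clarification: "the visit anchor date will be on or before a scheduled visit occurring after Week 16". The current text agrees with it.

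For Period 2, "Week 68 daily diary window construction for Period 2 will follow the exact same steps" as for Week 16.

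The endpoint concerned is secondary in the addendum (Protocol Section 4.2: "4-point improvement from baseline of JAHN(7) in Itch NRS at 16 weeks"; SAP APP.1.1.2) and in the main study at Week 16 (SAP Section 4.2). Itch over Weeks 52-68 is listed as exploratory in Table JAHN.6.7.

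**The concern.** Three features of the Step 2 sentence combine. It admits scheduled visits, its upper limit includes the later scheduled visit itself, and it takes the last visit that qualifies. A patient who missed Week 16 and attended Week 24 therefore has the Week 24 visit as anchor, even if an unscheduled visit took place a few days after the Week 16 date. The upper limit is also open, because the sentence does not say that the bounding visit is the next scheduled one.

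This conflicts with the section's own aim of a proximal unscheduled visit. It also conflicts with the extension sentence in Step 2 and with Step 3, both of which call the surrogate an unscheduled visit.

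What is at stake is the meaning of a value labelled Week 16. A late value enters as observed data, so neither nonresponder imputation nor mLOCF would mark it as a substitute. It reflects about 24 weeks on drug, possibly with topical corticosteroids added in between, while complete entries for the correct week go unused. Two programmers, one following the sentence and one following the aim, would derive different endpoints.

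**Working it through.** **Inputs.** Steps 1 to 3, the weekly diary grid and the 4-entry condition come from SAP Section 6.2.2. Visit weeks, the ±4-day tolerance and diary returns come from Protocol Attachment 1. Planned enrolment is 250 for the addendum (Protocol Section 4.4) and 1425 from the feeder studies (SAP Section 6.1).

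**1. Reproduce the plan's window.** On the weekly grid, Week w covers Days 7(w − 1) + 1 to 7w. For w = 16 this is 7 × 15 + 1 = 106 to 7 × 16 = 112, which matches Step 3. The nominal Week 16 visit is 16 × 7 + 1 = Day 113, and the 7 days before it are again Days 106-112.

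**2. Apply Step 2 literally.** Suppose there is no Week 16 visit and the diary is kept until Week 24. The nominal Week 24 visit is 24 × 7 + 1 = Day 169. It falls after Day 105 and on a scheduled visit after Week 16, so it is the anchor. The 7 days before it are Days 162-168, and 162 − 106 = 56 days late. With the ±4-day tolerance:

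| Week 24 visit | Window used | Delay |
|---|---|---|
| Day 165 | Days 158-164 | 52 days |
| Day 169 | Days 162-168 | 56 days |
| Day 173 | Days 166-172 | 60 days |

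Adding an unscheduled visit on Day 116 changes nothing under the literal rule. The window stays at Days 162-168 because the last visit wins.

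**3. Apply the 4-entry condition.** With the anchor on Day 169, the extended window reaches back 14 days to Day 155. With daily entries up to the stopping day:

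- Entries stop on or before Day 157: at most 3 fall in Days 155-168, Step 2 fails, and Step 3 gives Days 106-112 with no delay.
- Entries stop on Day 158: Days 155, 156, 157 and 158 make 4 entries, and the late window is accepted.
- Entries stop on Days 159-168: the late window is accepted in each case.

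**4. Can late entries exist?** Attachment 1 schedules diary return at Visit 4 (Week 16) and none at Visits 5 to 7. A patient who misses Visit 4 may still hold the device. The documents do not say whether entry is locked after Week 16.

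**5. Week 68.** Period 2 days count from the Week 52 visit. The next scheduled visit after Week 68 is Week 76, 24 weeks after Week 52, so again Day 169 with the same 56-day shift. Diary return is scheduled at Visit 12 (Week 68) and not at Visit 13 (Week 76).

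**6. Ceiling on numbers.** The documents give no missed-visit rate. Assume 1% to 5% miss Week 16 but attend Week 24, and that all of them keep making entries:

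- 250 × 0.01 = 2.5 and 250 × 0.05 = 12.5, about 3 to 13 patients.
- 1425 × 0.01 = 14.25 and 1425 × 0.05 = 71.25, about 14 to 71 patients.

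These are upper limits. The floor is zero, and the responder analysis is further restricted to baseline Itch NRS of 4 or more.

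**7. Test possible repairs.** Excluding only the later scheduled visit is not enough: an unscheduled visit on Day 160 would still give Days 153-159, and 153 − 106 = 47 days late. Requiring an unscheduled visit within ±4 days of Day 113 sends that patient to Step 3 (Days 106-112). A visit on Day 116 would give Days 109-115, which is 3 days later than nominal.

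**The case against.** The strongest reply is that the late window should rarely be filled. The SAP plans diary collection only to Week 16 in Period 1 and says the device is dispensed only until then. A late value needs a patient to miss Week 16, keep the device, go on making entries for about 8 unplanned weeks, and attend Week 24. Otherwise Step 3 returns the correct week. This stands. A reader might infer that every patient who missed the visit is measured late; the 4-entry condition rules that out.

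A reader might also infer that a secondary endpoint is at risk at Week 68. It is not: the secondary endpoints for Weeks 52-104 in SAP Section 4.2 contain no itch measure. Nor do the documents support a claim that the rule distorts the withdrawal comparison in a known direction. The Period 2 rule in SAP Section 6.4 censors efficacy data after retreatment, so any late Week 68 value could come only from patients not yet censored.

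The ±4-day limit in Section 6.2.2 governs assessments made at visits, while diary data have their own windows. Its absence from Step 2 is therefore not a contradiction, and here it serves only as an available yardstick.

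The addendum's Period 1 analysis is single-arm and descriptive, and its primary endpoint is IGA, which does not use the diary. That limits the consequence. It does not reconcile the Step 2 sentence with the aim stated in the same section.

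**Conclusion.** The rule is wrong as written. In a patient without a Week 16 visit who attended Week 24 and has at least 4 entries in the 7 to 14 days before it, the literal rule replaces Days 106-112 with about Days 162-168, even when the correct week is complete. The delay is 56 days, or 52 to 60 with visit tolerance. Without those entries there is no delay.

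The wording conflict and the size of the shift are firm. How often it happens is not known: the count may be zero, and the ceilings above rest on an assumed 1% to 5% and on continued diary use. The documents give no basis for the direction or size of any change in the itch response rate. The point concerns a secondary endpoint at Week 16 and exploratory analyses at Week 68. It should be corrected, but it does not touch the primary endpoint.

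**What to change.** Reword Step 2 so that the surrogate is the unscheduled visit closest to the nominal Week 16 date (Day 113), strictly before the next scheduled visit and within a stated proximity limit. The ±4 days already used in Section 6.2.2 for visit-based data is one option. If there is no such visit, go to Step 3 (Days 106-112, extendable to Day 99). Replacing only the inclusive upper limit by a strict one would leave late unscheduled visits eligible. Apply the same wording to Week 68.

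The SAP's Version 8 entry states that data to Week 104 are locked. The sponsor should therefore first check how the rule was programmed, report how many patients were anchored on a later visit at Week 16 and at Week 68, and re-derive the itch endpoint for any who were. If there were none, a clarifying sentence is enough.

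The cost is one changed rule, a small derivation re-run on locked data if needed, and possibly a few values that become missing and are imputed instead of being taken late.

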6.2.3. Analysis Methods

As few placebo patients are expected to be responders, no formal comparisons between treatment groups and placebo will be conducted for the responder and partial responder mITT populations. For the nonresponder mITT population, the following comparisons will be made for Period 1:

- for patients from originating monotherapy studies:
 - baricitinib 2 mg to baricitinib 4 mg versus baricitinib 2 mg to baricitinib 2 mg
 - baricitinib 1 mg to baricitinib 4 mg versus baricitinib 1 mg to baricitinib 2 mg
 - placebo to baricitinib 4 mg versus placebo to baricitinib 2 mg
- for patients from originating combination therapy study:
 - baricitinib 2 mg to baricitinib 4 mg versus baricitinib 2 mg to baricitinib 2 mg
 - placebo to baricitinib 4 mg versus placebo to baricitinib 2 mg

For the Period 2 substudy, the following treatment comparisons will be performed:

- for patients on baricitinib 4 mg in Period 1:
 - placebo versus baricitinib 4 mg
 - baricitinib 2 mg versus baricitinib 4 mg
- for patients on baricitinib 2 mg in Period 1:
 - placebo versus baricitinib 2 mg
 - baricitinib 1 mg versus baricitinib 2 mg

For Period 1, the main analysis method of categorical efficacy variables will use a logistic regression analysis with region, baseline disease severity from originating study (IGA 3 or IGA 4), baseline value from originating study, and treatment group in the model. For Period 2, the main analysis method of categorical efficacy variables will use a logistic regression analysis but with region, baseline disease severity at Week 52, baseline value at Week 52, and treatment

group in the model. In this case, the baseline disease severity at Week 52 can take values in 1 of 2 levels: 1) IGA of 0 or 1, and 2) IGA of 2. Firth's correction will be used in order to accommodate (potential) sparse response rates. The p-value for the odds ratio from the logistic regression model will be used for statistical inference, unless Firth's correction still results in quasi-separation. In that case, a Fisher's exact test p-value will be used for statistical inference. The difference in percentages and 100(1-alpha)% CI of the difference in percentages using the Newcombe-Wilson method without continuity correction will be reported.

For nonresponders, the main analysis method for all continuous efficacy variables will use MMRM analysis. The MMRM model will use a restricted maximum likelihood estimation. The model will include treatment, region, baseline disease severity (IGA), visit, and treatment-by-visit interaction as fixed categorical effects, and baseline and baseline-by-visit interaction as fixed continuous effects. For daily diary assessment endpoints, the model term 'visit' will include each of 16 weeks. An unstructured (co)variance structure will be used to model the between- and within-patient errors. If this analysis fails to converge, the heterogeneous autoregressive (ARH[1]), followed by the heterogeneous compound symmetry (CSH), followed by the heterogeneous Toeplitz, followed by autoregressive (AR[1]), followed by compound symmetry will be used. The Kenward-Roger method will be used to estimate the degrees of freedom. Treatment least square means (LSM) will be estimated within the framework of the MMRM using type 3 sums of squares. Differences in LSM between each dose of baricitinib and an appropriate comparator (and associated p-values, standard errors and 95% CI) will be used for statistical inference. The LSM difference, standard error, p-value, and 95% CI will be reported. For responders and partial responders, descriptive statistics will be provided for all continuous efficacy and health outcomes variables.

Treatment comparisons for select continuous efficacy and health outcomes variables may also be made using ANCOVA for primary and secondary objectives. For Period 1 analysis, when an ANCOVA model is used, the model includes region, baseline disease severity, treatment group, and baseline value. Treatment LSM will be estimated within the framework of the ANCOVA using type 3 sums of squares. Reported differences in LSM and associated p-values, standard errors, and 95% CI will be used for statistical inference. Analysis of covariance will be the primary method of analysis for continuous efficacy and health outcome variables for Period 2. In this Period, ANCOVA model includes region, baseline disease severity at Week 52, treatment group, and baseline value at Week 52. Baseline disease severity is defined previously.

Patients on baricitinib 2 mg or baricitinib 4 mg who are considered nonresponders (IGA >2) at entry into Study JAHN may respond with continued baricitinib treatment. Time to first response (IGA of ≤ 1) will be assessed using cumulative incidence functions for patients remaining on the same dose from the originating study. This will be used to determine when continued baricitinib treatment is futile. Missing IGA data will be replaced using the NRI rule.

For the US submission DBL (data cut-off 13Dec2019), all patients originating from Studies JAHL or JAHM are expected to have either reached the Week 52 visit or have discontinued from the study. Fisher's exact test will be used to test for differences between each baricitinib dose (including those that are randomized to a different dose) and placebo in proportions of patients

experiencing AEs) discontinuation from study drug, and for other categorical safety data. Continuous vital signs, body weight, and other continuous safety variables, including laboratory variables will be analyzed by an ANCOVA with treatment group and baseline value in the model. The significance of within-treatment-group changes from baseline will be evaluated by testing whether or not the treatment group LSM changes from baseline are different from zero; the standard error for the LSM change will also be displayed. Differences in LSM will be displayed, with the p-value associated with the LSM comparison to placebo or appropriate comparator and a 95% CI on the LSM difference also provided. In addition to the LSMs for each group, the within-group p-value for the change from baseline will be displayed.

6.2.4. *Derived Data*

- age (year), derived using first dose date as the reference start date and July 1st of birth year and truncated to a whole-year (integer) age. Patients whose derived age is <18 will have the required minimum age of 18 at informed consent confirmed; reporting for age, age groups, and lab ranges, however, will be based on their derived age.
- age group (<65, ≥65 years old)
- age group (<65, ≥65 to <75, ≥75 to <85, ≥85 years old)
- body mass index (BMI) (kg/m^2) = $\text{Weight (kg)} / (\text{Height [cm]} / 100)^2$
- BMI category (<25 kg/m^2 , ≥25 to <30 kg/m^2 , ≥30 kg/m^2)
- the duration of AD from diagnosis (years) = $([\text{Date of informed consent} - \text{Date of AD diagnosis}] + 1) / 365.25$
 - If year of onset is missing, duration of AD will be set as missing. Otherwise, unknown month will be taken as January, and unknown day will be taken as 01. The duration of AD will be rounded to 1 decimal place.
- duration of AD (years) category (0 to <2 years, 2 to <5 years, 5 to <10 years, 10 to <20 years, ≥20 years)
- diagnosis age (year), derived using diagnosis date as the reference start date and July 1st of birth year and truncated to a whole-integer age
- diagnosis age group (<18, ≥18 to <50, ≥50 years old)
- change from baseline = postbaseline measurement at Visit x – baseline measurement from originating study
 - If a baseline value is missing, it will not be imputed and the change from baseline will not be calculated.
- percent change from baseline at Visit x:

$$([\text{postbaseline measurement at Visit x} - \text{baseline measurement}] / \text{baseline measurement}) * 100$$
 - If a baseline value is missing, it will not be imputed and percent change from baseline will not be calculated.
- Weight (kg) = weight (lbs) * 0.454
- Weight category (<60 kg, ≥60 to <100 kg, ≥100 kg)
- Height (cm) = height (in) * 2.54
- cyclosporine inadequate efficacy prior to entry into originating study (yes, no)
 - Set to **yes** if the reason for discontinuation is inadequate response.

- cyclosporine intolerance prior to entry into originating study (yes, no)
 - Set to **yes** if the reasons for discontinuation are: intolerance to medication or contraindication (physician indicated cyclosporine was used and a contraindication was noted).
- cyclosporine contraindication (ineligible) prior to entry into originating study (yes, no)
 - Set to **yes** if cyclosporine was never used because of a contraindication.
- cyclosporine inadvisable prior to entry into originating study (yes, no)
 - Set to **yes** if the following reasons were selected for either not using the medication or discontinuing the medication:
 - reason for not using medication: physician decision, concern about side effects, unfavorable benefit risk, contraindication.
 - reasons for discontinuation: inadequate response, intolerance to medication, or contraindication.
- TCNI inadequate efficacy prior to entry into originating study (yes, no)
 - Set to **yes** if the reason for discontinuation is inadequate response.
- TCNI intolerance prior to entry into originating study (yes, no)
 - Set to **yes** if the reasons for discontinuation are: intolerance to medication or contraindication (physician indicated TCNI was used and a contraindication was noted).
- TCNI contraindication (ineligible) prior to entry into originating study (yes, no)
 - Set to **yes** if TCNI was never used because of a contraindication
- TCNI inadvisable prior to entry into originating study (yes, no)
 - Set to **yes** if the following reasons were selected for either not using the medication or discontinuing the medication:
 - reason for not using medication: physician decision, concern about side effects, unfavorable benefit risk, contraindication
 - reasons for discontinuation: inadequate response, intolerance to medication, or contraindication.

